9. APPENDICES

9.1. Details of Definitions of Endpoints

DLT Definitions

Previous anti-PD1 mAbs were administered in >1000 patients and were associated in the clinic with inflammatory adverse reactions resulting from increased or excessive immune activity (immune-mediated adverse reactions), likely to be related to the mechanism of action. Immune-mediated adverse reactions, which can be severe, may involve the gastrointestinal, skin, liver, endocrine, respiratory, renal or other organ systems.⁹

Severity of AEs will be graded according to CTCAE version 4.03. For the purpose of a dose finding decision, any of the following drug-related AEs occurring during the first cycle of treatment (21 days, or 28 days for subcutaneous administration) will be classified as DLTs following review by the investigators and the sponsor:

- Grade 5 AE.
- Hematologic toxicity:
 - Any Grade 4 hematologic AE, with the following clarifications.
 - Grade 4 neutropenia lasting >5 days from initiation of granulocyte-colony stimulating factor.
 - Grade 4 thrombocytopenia with bleeding.
 - Platelet transfusion requirement or a platelet count <10,000/uL.
- Non-Hematologic Toxicity:
 - Grade 4 non-hematologic AE.
 - Grade 3 AE lasting >7 days despite optimal supportive care.
 - Grade 3 central nervous system AE regardless of duration.
 - Concurrent aspartate aminotransferase (AST) or alanine aminotransferase (ALT) >3X upper limit of normal (ULN) and total bilirubin >2X ULN (potential Hy's law case see section Potential Cases of Drug-Induced Liver Injury).

The following AEs will not be adjudicated as DLTs:

- Any Grade 3 endocrinopathy that is adequately controlled by hormonal replacement.

- Grade 3 AE of tumor flare (defined as local pain, irritation, or rash localized at sites of known or suspected tumor).
- Isolated Grade 3-4 laboratory abnormalities that are not associated with clinical sequelae and are corrected with supplementation/appropriate management within 72 hours of their onset.
- Grade ≥ 3 infusion reactions and allergic reactions will not be considered dose limiting as they are unlikely to be dose related, but all available information on these events will be collected. If Grade ≥ 3 infusion reactions occur in ≥ 2 of the first 10 patients at any dose level, or if the occurrence is $\geq 5\%$ thereafter, a mandatory pre-treatment regimen for all new patients will be implemented. The incidence of Grade 1 and 2 reactions will also be taken into account. If a total rate of $>10\%$ all-grade infusion or allergic reactions is observed, a mandatory pre-treatment regimen for all new patients will be implemented.

Information regarding the DLT observation period can be found in the Criteria for Dose Finding (See protocol Section 3.1.4). For dose escalation, DLT observation is required for 21 days for IV infusion and 28 days for subcutaneous administration. However, DLT observation will continue for at least 120 days from first dose (or completion of 5 cycles, if still on treatment) to assess late immune-related dose-limiting AEs, and will be taken into account for MTD determination.

Late immune-related DLTs

Late immune-related DLTs are irAEs (see protocol Appendix 9) that meet the same grading criteria as DLT criteria but occur after the initial 21-Day DLT period for IV or 28-day DLT period for SC and during the first 120-day assessment period. Late immune-related DLTs will be added to the mTPI approach to reassess the dose-finding decisions.

For any patient being treated at dose levels that are subsequently considered to exceed the MTD, the option to reduce their dose will be discussed between the investigator and the sponsor's medical monitor. If the patient tolerated the above-MTD dose level well and is deriving clinical benefit, continuation of treatment at the above-MTD dose level will require re-consenting.

Maximum tolerated dose (MTD)

The maximum tolerated dose (MTD) is defined as the highest dose with true toxicity probabilities in the equivalence interval (EI) where the EI is defined as [22.5%-32.5%].

In practice, the MTD will be the highest dose associated with the occurrence of DLTs $\leq 33\%$ (eg, ≤ 3 of 9 evaluable patients experience a DLT during at least [90 days after the first dose]) or the first 5 treatment cycles if the patient remains on treatment.

Recommended Phase 2 Dose (RP2D) Definition

The recommended Phase 2 dose (RP2D) is the dose chosen for further study combining the MTD and OBD, based on Phase 1 study results, from the primary and secondary endpoints of the study. If the MTD proves to be clinically feasible for long-term administration in a reasonable number of patients, then this dose usually becomes the RP2D. Further experience with the MTD may result in a RP2D lower than the MTD. Next to safety assessment, careful consideration will be given to immunomodulatory effects, PK information, and preliminary anti-tumor activity. If an OBD can be determined, this will be a key factor in the determination of the RP2D.

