3.1.5. Dose-limiting Toxicity Definition

Previous anti-PD-1 mAbs were administered in >1000 patients and were associated in the clinic with inflammatory adverse reactions resulting from increased or excessive immune activity (immune-mediated adverse reactions), likely to be related to the mechanism of action. Immune-mediated adverse reactions, which can be severe, may involve the gastrointestinal, skin, liver, endocrine, respiratory, renal, or other organ systems.¹²

Severity of AEs will be graded according to CTCAE version 4.03. For the purpose of a dose finding decision, any of the following drug-related AEs occurring during the first cycle of treatment (21 days for IV, or 28 days for SC) will be classified as DLTs following review by the investigators and the sponsor:

- **Grade 5 AE**
- **Hematologic toxicity:**
 - Any Grade 4 hematologic AE, with the following clarifications:
 - Grade 4 neutropenia lasting >5 days from initiation of granulocyte-colony stimulating factor.

- Grade 4 thrombocytopenia with bleeding.
- Platelet transfusion requirement or a platelet count <10,000/uL.
- **Non-Hematologic Toxicity**
 - Grade 4 non-hematologic AE;
 - Grade 3 AE lasting >7 days despite optimal supportive care (see [Appendix 8](#));
 - Grade 3 central nervous system AE regardless of duration;
 - Meets criteria for drug-induced liver injury ([Section 8.6.2](#)).

The following AEs will not be adjudicated as DLTs:

- Any Grade 3 endocrinopathy that is adequately controlled by hormonal replacement.
- Grade 3 AE of tumor flare (defined as local pain, irritation, or rash localized at sites of known or suspected tumor).
- Isolated Grade 3-4 laboratory abnormalities that are not associated with clinical sequelae and are corrected with supplementation/appropriate management within 72 hours of their onset.
- Grade ≥ 3 infusion reactions and allergic reactions will not be considered dose limiting as they are unlikely to be dose related, but all available information on these events will be collected. If Grade ≥ 3 infusion reactions occur in ≥ 2 of the first 10 patients at any dose level, or if the occurrence is $\geq 5\%$ thereafter, a mandatory pre-treatment regimen for all new patients will be implemented. The incidence of Grade 1 and 2 reactions will also be taken into account. If a total rate of >10% all-grade infusion or allergic reactions is observed, a mandatory pre-treatment regimen for all new patients will be implemented.

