 - d. Hemoglobin ≥ 9 g/dL. Limited transfusions to reach this value are allowed, after discussion with sponsor's medical monitor. There should not be a chronic need for transfusions in the recent past (approximately 3 months).

8. Adequate Renal Function, as follows:
 - a. Serum creatinine ≤ 1.5 x upper limit of normal (ULN) or estimated creatinine clearance (CrCl) ≥ 40 mL/min as measured or calculated using the Cockcroft-Gault formula below:
 - Female CrCl = $[(140 - \text{age in years}) \times \text{weight in kg} \times 0.85] / [72 \times \text{serum creatinine in mg/dL}]$;
 - Male CrCl = $[(140 - \text{age in years}) \times \text{weight in kg} \times 1.00] / [72 \times \text{serum creatinine in mg/dL}]$;

If an estimated CrCl is believed to be inaccurate for a patient, 24-hour urine collection with actual assessment of CrCl is allowed.

9. Adequate Liver Function including:
 - a. Total serum bilirubin ≤ 1.5 x ULN except patients with Gilbert syndrome who should have total serum bilirubin < 3 x ULN;
 - b. Aspartate and alanine aminotransferase (AST & ALT) ≤ 3.0 x ULN.

10. Thyroid stimulating hormone (TSH) within normal limits (WNL) for institution; supplementation is acceptable to achieve a TSH WNL; in patients with abnormal TSH if Free T4 and Free Thyroxine Index are normal and patient is clinically euthyroid, patient is eligible.

11. International Normalized Ratio (INR) or activated partial prothrombin time (aPTT) < 1.5 x ULN.

12. Negative serum or urine pregnancy test (for women of childbearing potential) at screening and at the baseline visit (before the patient may receive the investigational product).

13. Male patients who are able to father children, and female patients of childbearing potential and at risk for pregnancy must agree to use 2 highly effective methods of contraception throughout the study and for at least 5 months after the last dose of assigned treatment.
14. Female patients who are not of childbearing potential as defined below, are eligible to be included (ie, meet at least one of the following criteria):
 - a. Have undergone a documented hysterectomy and/or bilateral oophorectomy;
 - b. Have medically confirmed ovarian failure; or
 - c. Achieved postmenopausal status, defined as follows: cessation of regular menses for at least 12 consecutive months with no alternative pathological or physiological cause; a serum follicle-stimulating hormone (FSH) level within the laboratory's reference range for postmenopausal women.

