8.6.2. Potential Cases of Drug-Induced Liver Injury

Abnormal values of AST and/or ALT levels concurrent with abnormal elevations in total bilirubin level that meet the criteria outlined below in the absence of other causes of liver

injury are considered potential cases of drug-induced liver injury (potential Hy's law cases) and should always be considered important medical events.

The threshold of laboratory abnormalities for a potential case of drug-induced liver injury depends on the patient's individual baseline values and underlying conditions. Patients who present with the following laboratory abnormalities should be evaluated further to definitively determine the etiology of the abnormal laboratory values:

- Patients with AST or ALT and total bilirubin baseline values within the normal range who subsequently present with AST or ALT values $\geq 3 \times \text{ULN}$ concurrent with a total bilirubin value $\geq 2 \times \text{ULN}$ with no evidence of hemolysis and an alkaline phosphatase value $\leq 2 \times \text{ULN}$ or not available.
- For patients with pre-existing ALT **OR** AST **OR** total bilirubin values above the ULN, the following threshold values should be used in the definition mentioned above:
 - For patients with pre-existing AST or ALT baseline values above the normal range, AST or ALT value ≥ 2 times the baseline values and $\geq 3 \times \text{ULN}$, or $\geq 8 \times \text{ULN}$ (whichever is smaller).

Concurrent with:

- For patients with pre-existing values of total bilirubin above the normal range: Total bilirubin level increased from baseline by an amount of at least $1 \times \text{ULN}$ **or** if the value reaches $\geq 3 \times \text{ULN}$ (whichever is smaller).

The patient should return to the investigational site and be evaluated as soon as possible, preferably within 48 hours from awareness of the abnormal results. This evaluation should include laboratory tests, detailed history, and physical assessment. The possibility of hepatic neoplasia (primary or secondary) should be considered.

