3. ENDPOINTS AND COVARIATES: DEFINITIONS AND CONVENTIONS

3.1. Primary Endpoint(s)

Part 1:

- *DLTs at escalated doses of PF-06801591.* The specific definition of DLT is provided in the study protocol.
- Adverse Events (AEs) as characterized by type, frequency, severity (as graded by National Cancer Institute Common Terminology Criteria for Adverse Events [NCI CTCAE] version 4.03), timing, seriousness, and relationship to study therapy PF-06801591.
- Laboratory abnormalities as characterized by type, frequency, severity (as graded by NCI CTCAE version 4.03), and timing.

Part 2:

- AEs as characterized by type, frequency, severity (as graded by NCI CTCAE version 4.03), timing, seriousness and relationship to study therapy PF-06801591 *administered by SC administration.*
- Laboratory abnormalities as characterized by type, frequency, severity (as graded by NCI CTCAE version 4.03) and timing.
- ORR as assessed using RECIST version 1.1 and irRECIST. ORR is defined as the proportion of patients who achieved completed response (CR) or partial response (PR) per RECIST 1.1, or irRECIST.

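### The liver DLT thresholds restated in SAP 9.1 contradict Protocol 8.6.2, the section that defines the liver DLT and that the SAP itself points to

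*SAP*

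**What the plan says.** Protocol 3.1.5 lists, among the non-hematologic DLTs, an event that "Meets criteria for drug-induced liver injury" and refers to Section 8.6.2. That section opens from the principle that "The threshold of laboratory abnormalities for a potential case of drug-induced liver injury depends on the patient's individual baseline values and underlying conditions".

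- **AST/ALT and bilirubin normal at entry:** AST or ALT ≥3x ULN with total bilirubin ≥2x ULN, no hemolysis, and ALP ≤2x ULN or not available.
- **AST/ALT above ULN at entry:** at least twice baseline and ≥3x ULN, or ≥8x ULN, whichever is smaller.
- **Bilirubin above ULN at entry:** "Total bilirubin level increased from baseline by an amount of at least" 1x ULN, or a value ≥3x ULN, whichever is smaller.

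The two raised-baseline rules replace the thresholds inside the first definition, so its hemolysis and ALP conditions carry over.

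SAP 3.1 states that "The specific definition of DLT is provided in the study protocol". SAP 9.1 nevertheless restates the liver item as "Concurrent aspartate aminotransferase (AST) or alanine aminotransferase (ALT) >3X upper limit of normal (ULN) and total bilirubin >2X ULN", labels it a potential Hy's law case, and adds "see section Potential Cases of Drug-Induced Liver Injury". The SAP has no section of that name; Protocol 8.6.2 does. The lead-in to the SAP list limits DLTs to "any of the following drug-related AEs occurring during the first cycle of treatment", classified after review by investigators and sponsor. Protocol 3.1.5 has the same gate.

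Part 1 eligibility (Protocol 4.1.1) admits AST and ALT up to 3.0x ULN and total bilirubin up to 1.5x ULN, "except patients with Gilbert syndrome who should have total serum bilirubin" below 3x ULN. It sets no ALP limit.

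**The concern.** DLT is a Part 1 primary endpoint and the only input to the mTPI decision table. The SAP gives a programmer or reviewer two numbers that apply to all patients. The protocol gives a rule that depends on baseline and carries two further conditions. Eligibility admits patients whose entry values lie where the two rules part.

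If the SAP numbers are used for the DLT summary, events can be counted that the protocol does not count. SAP 6.2.1 summarizes and lists DLTs by dose level, and late immune-related DLTs judged on the same criteria are fed back into the mTPI. In the text available, neither the protocol's summary of changes nor the SAP version history mentions a change to the liver criterion. SAP Section 2 says that major modifications of the primary endpoint definition will also appear in a protocol amendment.

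**Working it through.** No figure in the plan rests on the liver threshold, so there is nothing to reproduce. The check applies both texts to the entry values that Part 1 allows. All values are multiples of ULN, and b is the entry value.

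**Rules**

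- SAP 9.1: AST/ALT >3 and bilirubin >2, whatever b is.
- Protocol 8.6.2, AST/ALT: 3 if b is normal, otherwise min(max(2b, 3), 8).
- Protocol 8.6.2, bilirubin: 2 if b is normal, otherwise min(b + 1, 3).
- Protocol 8.6.2 also requires no hemolysis, and ALP ≤2 or not available.

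**Thresholds**

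| Test | Entry value | SAP needs | Protocol needs |
|---|---|---|---|
| AST/ALT | 1.0 | >3 | ≥3 |
| AST/ALT | 1.5 | >3 | ≥3 |
| AST/ALT | 2.0 | >3 | ≥4 |
| AST/ALT | 2.5 | >3 | ≥5 |
| AST/ALT | 3.0 | >3 | ≥6 |
| Bilirubin | 1.0 | >2 | ≥2.0 |
| Bilirubin | 1.2 | >2 | ≥2.2 |
| Bilirubin | 1.5 | >2 | ≥2.5 |
| Bilirubin (Gilbert) | 2.0 | >2 | ≥3.0 |
| Bilirubin (Gilbert) | 2.5 | >2 | ≥3.0 |
| Bilirubin (Gilbert) | 2.9 | >2 | ≥3.0 |

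The protocol threshold is never below 3 for AST/ALT or below 2 for bilirubin. Apart from values exactly at 3 or 2 (> against ≥), every event that meets the protocol also meets the SAP. The reverse is not true, so any discrepancy adds DLTs under the SAP.

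**Events on which the texts disagree**

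| Case | SAP 9.1 | Protocol 8.6.2 |
|---|---|---|
| A. Normal entry values, then AST 4, bilirubin 2.5, ALP 3 | Met (4 > 3, 2.5 > 2) | Not met (ALP 3 > 2) |
| B. No Gilbert syndrome: AST 3.0 to 3.5, bilirubin 1.5 to 2.1 | Met | Not met (needs 2 × 3.0 = 6.0 and 1.5 + 1 = 2.5) |
| C. Gilbert syndrome: AST 2.9 to 3.1, bilirubin unchanged at 2.5 | Met | Not met (needs 2 × 2.9 = 5.8 and min(3.5, 3) = 3.0) |

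In the hepatic table of Protocol Appendix 8, AST above 3 up to 5 and bilirubin above 1.5 up to 3 are Grade 2. The AST and bilirubin values in all three cases fall there. They therefore trigger neither the Grade 3 and Grade 4 DLT items nor the exclusion for isolated Grade 3-4 laboratory abnormalities. The liver item alone decides.

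**How much change is needed**

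- Case B limits: at entry AST 3.0, any rise passes the SAP's AST limit. Bilirubin must still go from 1.5 to above 2.0, a rise of more than 0.5/1.5 = 33%. The protocol needs +100% in AST and 1.0/1.5 = +67% in bilirubin.
- Case C: AST rises by 3.1/2.9 − 1 = 7%, and bilirubin does not change.

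**Effect of one extra DLT** (Protocol Table 3, identical to SAP Table 1)

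- 0/3 escalate becomes 1/3 stay.
- 1/3 stay becomes 2/3 de-escalate.
- 1/6 escalate becomes 2/6 stay.
- 2/4 stay becomes 3/4 unacceptable.

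For the MTD, Protocol 3.1.6 gives up to 3 of 9 as its example of an acceptable count. One more is 4/9 = 44%, above the 33% limit.

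**The case against.** The strongest reply is that the SAP defers to the protocol twice: in SAP 3.1, and in the liver bullet itself through its pointer to the section title. On that reading the numbers are shorthand for a Hy's law case and the protocol governs. This has force. A reader might infer that the SAP replaces the protocol rule, and the documents do not support that. What they contain is a restatement that disagrees with its own source. The pointer does not remove the conflict, because the explicit numbers remain and differ from the section named. It also gives no document or section number, whereas SAP 9.1 does name the protocol when it cites Section 3.1.4 for the observation period.

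A reader might also infer that eligible patients in general could become DLTs with almost no change in their liver tests. That does not hold. Outside Gilbert syndrome bilirubin must rise by more than a third even at the entry limit. Near-zero change in both tests is possible only for a Gilbert patient with bilirubin already above 2x ULN and AST/ALT near 3x ULN.

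Crossing the threshold is also not enough, since the event must be judged drug-related and be reviewed. A cholestatic rise put down to liver metastases, or a bilirubin level present before dosing, may fail that test. This narrows the number of affected events, but the reviewers still need one criterion to apply.

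The ALP difference matters only when ALP is measured and exceeds 2x ULN, because the protocol accepts a missing value. ALP is, however, in the routine chemistry panel (Protocol Table 4).

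Finally, dose-finding runs under the protocol, and Protocol 3.1.8 records that 300 mg SC had already been selected for Part 2. The Table 3 shifts show what one DLT can do, not that this sentence drove a decision.

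**Conclusion.** The point stands as a contradiction on a Part 1 primary-endpoint rule. SAP 9.1 states a fixed liver criterion. Protocol 3.1.5, through 8.6.2, states one that depends on baseline and excludes hemolysis and, where measured, ALP above 2x ULN. The discrepancy runs one way, apart from exact equality: toward extra DLTs under the SAP.

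One reclassified event is enough to change a Table 3 cell. With the Part 2 dose already chosen, the more likely effect is on the reported DLT table and the MTD statement.

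This assumes that the event has been judged drug-related and reviewed, and that the SAP numbers are applied as written. How many patients it touches cannot be computed, because the documents give neither the distribution of baseline liver tests nor the share of patients with Gilbert syndrome. The SAP says it is based on protocol Amendment 3, while the protocol at hand is Amendment 4. The wording may have been carried over, but the documents do not say so. No view is taken on which clinical threshold is right.

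**What to change.** Reconcile SAP 9.1 with Protocol 3.1.5 and 8.6.2 so that one liver DLT criterion applies. One way is to delete the restated thresholds and cite Protocol Section 8.6.2 by number, which carries out what SAP 3.1 already says. If the sponsor instead intends the SAP's numbers, SAP Section 2 implies a protocol amendment where the change is a major modification of the primary endpoint definition. The first route costs one line in the SAP.

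If any DLT listing has already been produced, check each drug-related event with AST or ALT at or above 3x ULN together with bilirubin at or above 2x ULN against the reconciled text, and report any change in classification.

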9.2. Time to Event Data Analysis Censoring Rules

Table 9.2.1: Progression Free Survival and Duration of Response

Situation	Date of Progression/Censoring¹	Outcome
Inadequate baseline assessment	First dosing date in Cycle 1	Censored
No on-study assessments	First dosing date in Cycle 1	Censored
Alive over the course of the study and no progression	Date of last objective tumor assessment	Censored
Progression or death documented on or between scheduled tumor assessments	Date of first objective tumor assessment showing objective progression or death date	Progressed/Death (Event)
Treatment discontinuation for undocumented progression	Date of last objective tumor assessment	Censored
Treatment discontinuation due to toxicity or other reason	Date of last objective tumor assessment	Censored
Progression/Death prior to second planned tumor	Date of death	Progressed/Death (Event)
Death or progression after 2 or more missed tumor assessments	Date of last objective tumor assessment prior to the event	Censored

1. For date of censorship, if a tumor assessment takes place over a number of days (eg, superficial lesions one day, scans another), the last date is used as the assessment date.
2. The first two reasons (Inadequate baseline assessment; No on-study assessments) are not applicable for Duration of Response, as that endpoint is only for the subset of responders.

Table 9.2.2: Time to Progression

Situation	Date of Progression/Censoring¹	Outcome
Inadequate baseline assessment	First dosing date in Cycle 1	Censored
No on-study assessments	First dosing date in Cycle 1	Censored
Alive over the course of the study and no progression	Date of last objective tumor assessment	Censored
Progression Documented on or between scheduled tumor assessments	Date of first objective tumor assessment showing objective progression	Progressed (Event)
Treatment discontinuation for undocumented progression	Date of last objective tumor assessment	Censored

Situation	Date of Progression/Censoring¹	Outcome
Treatment discontinuation due to toxicity or other reason	Date of last objective tumor assessment	Censored
New anticancer treatment prior to documented progression	Date of last objective tumor assessment prior to new anticancer treatment	Censored
Death prior to first planned tumor assessment	Start date (C1D1)	Censored
Death without objective progression	Date of last objective tumor assessment prior to death	Censored
Progression after 2 or more missed tumor assessments	Date of last objective tumor assessment prior to the event	Censored

3. For censoring date, if a tumor assessment takes place over a number of days (eg, superficial lesions one day, scans another), the last date is used as the assessment date.

